If this application involves the use of a HUD "humanitarian" device: describe whether the use is for "on-label" clinical patient care, "off-label" clinical patient care, and/or research (collecting safety and/or effectiveness data).

This quality improvement research study aims to improve the utilization of genetic counseling and testing among providers at Olympic Medical Center (OMC) who are caring for their cancer patients in a rural and underserved area. SCCA will coach the OMC providers to offer eligible patients genetic counseling and testing in order to increase access and help the OMC site meet genetic recommendations and guidelines. Specifically, this study aims to (1) review and develop OMC's clinical operations workflow to identify cancer patients who meets criteria for genetic counseling and testing; (2) measure uptake of genetic testing; and (3) document clinical and patient reported outcomes following genetic test results.

1.6 Study design. Provide a one-sentence description of the general study design and/or type of methodology.

Your answer will help HSD in assigning applications to reviewers and in managing workload. Examples: a longitudinal observational study; a double-blind, placebo-controlled randomized study; ethnographic interviews; web scraping from a convenience sample of blogs; medical record review; coordinating center for a multi-site study.

This is a quality improvement research study in which SCCA will provide coaching to OMC providers to offer genetic counseling and testing in order to address current gaps in caring for their high-risk patients.

1.7 Intent. Check all the descriptors that apply to your activity. You must place an "X" in at least one box.

This question is essential for ensuring that your application is correctly reviewed. Please read each option carefully.

Descriptor

- 1. Class project or other activity whose purpose is to provide an educational experience for the researcher (for example, to learn about the process or methods of doing research).
- 2. Part of an institution, organization, or program's own internal operational monitoring.

Document Date & Version

11/15/2019

Version 2.2

#2003

[name]

5/4/2020

Version 1

Page 3 of 46

3. Improve the quality of service provided by a specific institution, organization, or program.

4. Designed to expand the knowledge base of a scientific discipline or other scholarly field of study, and produce results that:

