Phase 2: The second phase involves a tiered intervention in which SCCA subject matter experts will coach the OMC providers to provide guidance on providing genetic counseling and testing to their patients. Involvement in this study does not dictate how the OMC providers carry out clinical care, so it is up to the OMC providers to decide whether or not to implement the coaching in their practice. First, patients and their families fill out the standardized FHQ before their initial appointment, which will be sent via email by the team at OMC. OMC will gather the same patient information described in Phase 1 which will then be sent directly to the study's research coordinator at SCCA, where the research coordinator will follow the same data storage, participant ID assignment, and distribution processes as in Phase 1. SCCA subject matter experts would then review this information with the OMC providers at bi-monthly virtual conferences before patients come for their initial visit at OMC. For patients who meet NCCN criteria, the oncology team at OMC would include in their initial visit workflow to discuss importance of cancer risk assessment and offer genetic testing. For the patients with a more complicated history, the OMC team would offer a referral to the SCCA for a complete cancer risk assessment evaluation.

At the end of phase 2, SCCA subject matter experts will measure how many patients met NCCN criteria for testing how many patients were referred to genetic counseling and how many either had a test online or were seen at UWMC and the SCCA for a genetic evaluation. This data will then be compared with phase 1 data to measure the effectiveness of SCCA's coaching for OMC's providers as well as quality improvement of their processes.

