	Eovist / Primovist	Gadoxetate disodium	Linear
	Gadavist	Gadobutro	Macrocyclic
	Magnevist	Gadpentetate dimeglumine	Linear
	MultiHance	Gadobenate dimeglumine	Linear
	Omniscan	Gadodiamide	Linear
	OptiMARK	Gadoversetamide	Linear
	ProHance	Gadoteridol	Macrocyclic
	Other, provide name:		

- 1.) The FDA has concluded that gadolinium is retained in the body and brain for a significantly longer time than previously recognized, especially for linear GBCAs. The health-related risks of this longer retention are not yet clearly established. However, the UW IRB expects researchers to provide a compelling justification for using a linear GBCA instead of a macrocyclic GBCA, to manage the risks associated with GBCAs.

Describe why it is important to use a GBCA with the MRI scan(s). Describe the dose that will be used and (if it is more than the standard clinical dose recommended by the manufacturer) why it is necessary to use a higher dose. If a linear GBCA will be used, explain why a macrocyclic GBCA cannot be used.

- 2.) Information for subjects. Confirm by checking this box that subjects will be provided with the FDA-approved Patient Medication Guide for the GBCA being used in the research or that the same information will be inserted into the consent form.

Confirmed

c. **MRI facility.** At which facility(ies) will the MRI scans occur? Check all that apply.

- UWMC Radiology/Imaging Services (the UWMC clinical facility)
- DISC Diagnostic Imaging Sciences Center (UWMC research facility)
- BMIC Biomolecular Imaging Center (South Lake Union research facility)
- Harborview Radiology/Imaging Services (the Harborview clinical facility)
- SCCA Imaging Services
- Northwest Diagnostic Imaging
- Other: identify in the text box below:

Personnel. For MRI scans that will be conducted at the DISC or BMIC research facilities: The role, qualifications, and training of individuals who will operate the scanner, administer the GBCA (if applicable), and/or insert and remove the IV catheter should be described in question **12.3**.

5.4 Data variables. Describe the specific data that will be obtained (including a description of the most sensitive items). Alternatively, a list of the data variables may be uploaded to **Zipline**.

OMC clinic outcomes data: report including the number of patients seen at OMC with a diagnosis of breast, ovarian, prostate, colon, and pancreatic cancer

OMC patients' Family History Questionnaire responses

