10 RISK / BENEFIT ASSESSMENT

10.1 **Anticipated risks.** Describe the reasonably foreseeable risks of harm, discomforts, and hazards to the subjects and others of the research procedures. For each harm, discomfort, or hazard:

- Describe the magnitude, probability, duration, and/or reversibility of the harm, discomfort, or hazard, AND
- Describe how the risks will be reduced or managed. Do not describe data security protections here, these are already described in Question 9.6.
- Consider possible physical, psychological, social, legal, and economic harms, including possible negative effects on financial standing, employability, insurability, educational advancement or reputation. For example, a breach of confidentiality might have these effects.
- Examples of "others": embryo, fetus, or nursing child; family members; a specific group.
- Do not include the risks of non-research procedures that are already being performed.
- If the study design specifies that subjects will be assigned to a specific condition or intervention, then the condition or intervention is a research procedure - even if it is a standard of care.
- Examples of mitigation strategies: inclusion/exclusion criteria; applying appropriate data security measures to prevent unauthorized access to individually identifiable data; coding data; taking blood samples to monitor something that indicates drug toxicity.
- As with all questions on this application, you may refer to uploaded documents.

Participation in this study involves a time commitment from the OMC provider subjects in which they are required to designate time from their schedule to participate in bi-monthly virtual conferences. If a participant decides to implement the coaching from SCCA in their clinical care, time will be required to discuss genetic counseling and testing with their eligible patients, ordering genetic testing, and allocating extra time at patient follow-up visits to review genetic results. This time commitment may cause stress in the OMC provider subjects because it will likely require them to change how they manage their schedules.

This study requires OMC provider subjects to grant permissions to SCCA to collect their patients' medical records, which may pose security concerns and a breach of confidentiality for their patients.

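### The count that Section 5.1 compares between phases mixes tests with visits and does not name OMC-ordered tests, so it is not a clean measure of testing uptake (Aim 2)

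*Protocol*

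**What the plan says.** Aim 2 in Section 1.5 is to "measure uptake of genetic testing".

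Section 5.1 lists the same three counts for each phase: patients who met NCCN criteria, patients referred to genetic counseling, and "how many either had a test online or were seen at UWMC and the SCCA for a genetic evaluation". It then states their use: "This data will then be compared with phase 1 data to measure the effectiveness of" the coaching.

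The Phase 2 pathway in 5.1 has two branches. When a patient fulfils the NCCN testing criteria, the protocol says "the oncology team at OMC would include in their initial visit workflow to discuss importance of cancer risk assessment and offer genetic testing". Where the history is more complicated, it says "the OMC team would offer a referral to the SCCA for a complete cancer risk assessment evaluation". Adoption is voluntary: "it is up to the OMC providers to decide whether or not to implement the coaching in their practice". Section 10.1 expects providers who adopt the coaching to spend time on "ordering genetic testing, and allocating extra time at patient follow-up visits to review genetic results".

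Section 10.10 describes the outcomes differently. In 10.10.c, completed appointments and test results are separate tracked items. In 10.10.d, four numbers are to be reported to providers after each phase: eligible patients, those referred, those who completed a genetics appointment, and those who chose testing.

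Section 5.4 describes the clinic outcomes data as a "report including the number of patients seen at OMC with a diagnosis of breast, ovarian, prostate, colon, and pancreatic cancer". It names neither a completed test nor its route, though the form allows a separate variable list.

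**The concern.** The third count in 5.1 is the only one of the three that includes a testing event, so the phase comparison must rely on it for Aim 2. It has three faults for that purpose.

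1. It joins a test and a visit with either/or. A patient seen but never tested scores the same as a patient tested.
2. The online test appears only in these two sentences of 5.1 and is never defined. It may or may not include a test that an OMC provider orders.
3. Tests ordered at OMC are not named, although testing at the initial OMC visit is what the coaching is meant to increase.

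At stake is the pilot's reading of whether coaching raised testing. The change in the pooled count equals the change in testing only if visits without a test, and OMC orders not scored as online, both stay constant or offset each other. Phase 2 acts on both.

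**Working it through.** The protocol states no rates, effect size or power for this measure, so there is no figure to reproduce. The check is algebra followed by illustration. **Every rate below is an assumption.**

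**Notation, per NCCN-eligible patient**
- s = proportion seen at UWMC/SCCA
- v = share of those visits that lead to a test
- o = proportion tested by OMC order
- phi = share of OMC orders scored as an online test
- subscripts 1 and 2 = phase

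Simplifications: s and o do not overlap; v and phi are equal in both phases; patient-initiated online tests are equal in both phases and cancel.

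**Formulas**
- Counted under 5.1 = s + phi × o
- Actually tested = v × s + o
- Bias = change in counted − change in tested = (1 − v)(s2 − s1) − (1 − phi)(o2 − o1)

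The first term is the change in visits without a test. The second is the change in OMC orders that go uncounted.

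**Range.** Take s1 = 0.18, s2 from 0.10 to 0.38, o2 − o1 from 0 to 0.30, and v from 0.6 to 1. The lower extreme is 0.4 × (0.10 − 0.18) − (1 − phi) × 0.30. The upper is 0.4 × (0.38 − 0.18) − 0.

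| phi | Lowest bias | Highest bias |
|---|---|---|
| 0 | −0.032 − 0.300 = −0.332 | +0.080 |
| 0.5 | −0.032 − 0.150 = −0.182 | +0.080 |
| 1 | −0.032 − 0 = −0.032 | +0.080 |

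**Three cases at v = 0.8, phi = 0**

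| Case | s | o | Counted | Tested | Bias |
|---|---|---|---|---|---|
| A | 18% to 18% | 10% to 40% | 18% to 18% (0) | 24.4% to 54.4% (+30) | −30 points |
| B | 18% to 38% | 10% to 10% | 18% to 38% (+20) | 24.4% to 40.4% (+16) | +4 points |
| C | 18% to 28% | 10% to 12% | 18% to 28% (+10) | 24.4% to 34.4% (+10) | 0 |

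For example, tested in A is 0.8 × 0.18 + 0.10 = 0.244 in Phase 1 and 0.8 × 0.18 + 0.40 = 0.544 in Phase 2. The bias in A shrinks to −15 points at phi = 0.5 and to 0 at phi = 1.

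**Break-even.** For a 10-point rise in visits at v = 0.8, visits without a test rise by 0.2 × 10 = 2 points. The bias is nil if OMC orders rise by 2 points (phi = 0) or 2 / 0.5 = 4 points (phi = 0.5). A larger rise gives understatement, a smaller one overstatement.

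**In patients.** Section 2.7 gives 60/120 as the maximum per phase. If 20% to 60% of 60 are eligible (assumed), that is 12 to 36 patients. A then misses 0.30 × 12 = 3.6 to 0.30 × 36 = 10.8 tests. B adds 0.04 × 12 = 0.5 to 0.04 × 36 = 1.4.

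**Separate illustration of direction.** Assume 5% online tests in both phases, visits 20% then 10% with 80% tested, and OMC orders 0% then 30%.
- Tested: 5 + 16 = 21%, then 5 + 8 + 30 = 43%.
- 5.1 count without OMC orders: 5 + 20 = 25%, then 5 + 10 = 15%.
- 5.1 count with OMC orders: 25%, then 5 + 10 + 30 = 45%.

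Testing doubles, while the 5.1 count falls or rises according only to how the undefined phrase is read.

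**The case against.** The strongest reply is that the needed measure is already planned. Section 10.10.d has a separate testing count after both phases, with no limit on route, and 10.10.c says test results are tracked. On this view 5.1 is loose lay wording, possibly meaning two separate tallies. It never ties its third count to Aim 2, and it serves a broader purpose that covers counseling as well as testing. The remedy would then be a definition and a cross-reference.

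Part of this stands. The pooled count is one of three, and the protocol does plan a count that could serve Aim 2. Section 5.4 is not exhaustive, so its silence does not prove that the item is missing. All rates are assumed, and the bias range spans zero. If every OMC order is scored as online, only the mixing of tests and visits matters: at most +8 points, or about 1 to 3 patients among 12 to 36 eligible. The reversal of direction assumes that UWMC/SCCA visits halve, which the protocol does not predict; its Phase 2 adds an offer of SCCA referral.

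It does not remove the point. Section 5.1 names the data that will judge the coaching, and as written those data contain no testing count. Read as two tallies, the sentence would still leave the online test undefined and OMC orders unnamed. Section 10.10.d has its own ambiguity: each number is chained to the group before it, so a test may count only after a referral and a genetics appointment. That reading would again drop tests ordered directly at OMC. The protocol itself fixes the measure in two different ways, so this is not detail left to an analysis plan.

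**Conclusion.** The concern holds and should be fixed. Following 5.1 as written can misstate the change in testing uptake between phases. It understates the change if uncounted OMC orders rise more than visits without a test, and overstates it if the reverse is true. Which applies depends on the meaning of an online test and on how far providers adopt the coaching, which the protocol leaves to them.

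The actual size cannot be determined from the protocol. Under the assumed ranges, the potential understatement is much larger than the overstatement unless most OMC orders are scored as online. Confidence is medium, because the wording faults are plain in the text but their effect rests on assumed rates and on an undefined phrase.

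**What to change.** - In 5.1, make the uptake comparison for both phases the number of NCCN-eligible patients with a germline test completed by any route: OMC-ordered, online, or through UWMC/SCCA.
- Report completed UWMC/SCCA visits and referrals as separate counts. Keep referrals as a process measure, read alongside on-site testing, because on-site testing can replace referral.
- Define an online test, and say whether it includes orders placed by OMC providers.
- In 10.10.d, use the same eligible-patient denominator and state that a test counts whether or not a genetics appointment took place.
- In 5.4, list test completed and its route, collected identically in both phases. Settle the definition before Phase 1 data are abstracted, since Phase 1 is the comparator.

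The cost is wording in 5.1 and 10.10.d and one chart field with minor abstraction work. Section 10.10.c says test results are already to be recorded and tracked, so this may largely formalise existing tracking. It needs no extra patients or visits.

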Phase 1: Patients in the observational group in which SCCA collects data on OMC patients who follow their current processes (without intervention)	60/120
Phase 2: Patients in the monitoring group in which SCCA collect data on OMC patients who follow the tiered intervention (OMC providers receive coaching from SCCA subject matter experts)	60/120

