5 PROCEDURES

5.1 Study procedures.

Using lay language, provide a complete description of the study procedures, including the sequence, intervention or manipulation (if any), drug dosing information (if any), use of records, time required, and setting/location. If it is available: Upload a study flow sheet or table to [Zipline](#).

For studies comparing standards of care: It is important to accurately identify the research procedures. See UW IRB [POLICY: Risks of Harm from Standard Care](#) and the draft guidance from the federal Office of Human Research Protections, ["Guidance on Disclosing Reasonably Foreseeable Risks in Research Evaluating Standards of Care"](#); October 20, 2014.

This quality improvement research study is designed in two phases, each phase is done over a 3-month period for a total study duration of 6 months. The SCCA study team will be enrolling eligible OMC providers who will handle all patient interaction and communication.

Phase 1: The first phase does not involve intervention; OMC will be following their existing processes. OMC will gather identified data on the patient's clinic diagnosis and stage, pathology report features, and treatment options for patients with the above diagnose and offer patients the option to fill out a standardized Family History Questionnaire (FHQ) on the day of their initial visit if they decide to do so. The FHQ will be offered as part of clinical care up to the discretion of the OMC providers. OMC will also gather de-identified data on the number of patients seen with a diagnosis of breast, ovarian, prostate, colon, and pancreatic cancer. The above data will then be sent to the study's research coordinator at SCCA (through secure email) which will be stored in a secured J-Drive folder within the SCCA network. The research coordinator will randomly assign all identified patient data to a unique participant ID before distributing to SCCA subject matter experts (cancer geneticist and/or genetic counselor) for review. From OMC's collected data, SCCA subject matter experts will measure how many patients met NCCN criteria for testing how many patients were referred to genetic counseling and how many either had a test online or were seen at UWMC and the SCCA for a genetic evaluation.

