a.3. Explain which results will not be offered to subjects and provide the rationale for not offering these results.

Reasons not to offer the results might include:

- *There are serious questions regarding validity or reliability*
- *Returning the results has the potential to cause bias*
- *There are insufficient resources to communicate the results effectively and appropriately*
- *Knowledge of the result could cause psychosocial harm to subjects*

b. What is the plan (if any) for offering subjects any results that are not clinically actionable?

Examples: non-actionable genetic results, clinical tests in the normal range, experimental and/or uncertain results.

	No
	Yes

→ If yes, explain which results will be offered to subjects and provide the rationale for offering these results.

c. Describe the validity and reliability of any results that will be offered to subjects.

The IRB will consider evidence of validity such as studies demonstrating diagnostic, prognostic, or predictive value, use of confirmatory testing, and quality management systems.

The results that will be offered to the OMC provider subjects will be reliable due to the consistent, uniform processes in data collection and recommendation that will be followed throughout the entire course of this study. The results will be valid because the reporting of the numbers of patients meeting criteria, referrals for genetic counseling/testing, completed genetics appointments, and genetic testing results, will be recorded and tracked by the same research coordinator.

d. Describe the process for communicating results to subjects and facilitating understanding of the results. In the description, include who will approach the participant with regard to the offer of results, who will communicate the result (if different), the circumstances, timing, and communication methods that will be used.

Results will be communicated to the OMC provider subjects at the end of phase 1 and phase 2. The SCCA study team and subjects will meet to discuss the number of patients seen who were eligible for genetic testing, number of those patients who were referred for genetic counseling/testing, the number of those patients who complete a genetics appointment, and the number of those patients who chose to undergo genetic testing. The OMC provider subjects will also be sent this data for their review in order to assess their current clinic processes.

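### Section 5.1 presents the Phase 2 versus Phase 1 comparison as measuring the effectiveness of coaching, but the family history questionnaire procedure and feedback of Phase 1 counts change at the same boundary, so only a before-after change under the whole package can be described

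*Protocol*

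**What the plan says.** Section 5.1 sets out two phases of 3 months each, 6 months in total. Phase 1 follows OMC's existing processes. Phase 2 is a tiered intervention, after which the same quantities are counted again: patients meeting NCCN criteria, patients referred, and patients tested or seen for evaluation. On the purpose, 5.1 states: "This data will then be compared with phase 1 data to measure the effectiveness of" SCCA's coaching, and in the same sentence names quality improvement of OMC's processes. Section 2.7 describes what the Phase 2 group follows as the "tiered intervention (OMC providers receive coaching from SCCA subject matter experts".

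Two other things differ between the phases.

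- **FHQ.** In Phase 1 it is an option on the day of the first visit: "The FHQ will be offered as part of clinical care up to the discretion of the OMC providers". In Phase 2 it opens the sequence: "First, patients and their families fill out the standardized FHQ before their initial appointment, which will be sent via email". Section 5.14 gives its purpose as identifying patients eligible for counseling and testing.
- **Feedback.** Section 10.10.d says: "Results will be communicated to the OMC provider subjects at the end of phase 1 and phase 2". The counts are nested, running from patients eligible for testing to the "number of those patients who were referred for genetic counseling/testing", and on to those who complete an appointment and those tested. It adds: "The OMC provider subjects will also be sent this data for their review in order to assess their current clinic processes".

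Section 10.10.c rests the reliability of these results on "consistent, uniform processes in data collection and recommendation that will be followed throughout the entire course of this study".

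**The concern.** Part of the stated purpose is to attribute the Phase 2 minus Phase 1 difference to coaching. That attribution needs coaching to be the only relevant thing that changes, or a comparison group that receives everything else. Neither condition is met. Section 5.1 also leaves each provider free to decide whether to act on the coaching. Phase 2 could therefore include the emailed FHQ and the feedback with little uptake of coaching, and the comparison would still be described as measuring coaching.

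The FHQ change raises a second, measurement issue. It can change how many patients are recognised as meeting NCCN criteria. For the nested counts in 10.10.d, that number is the denominator of any proportion formed from them. At stake is what the study may conclude: an effect of coaching, or a before-after change under everything introduced in Phase 2.

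**Working it through.** The protocol gives no effect size, test or baseline rate for this comparison, so there is no figure to reproduce.

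**1. What changes at the boundary**

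| Element | Phase 1 | Phase 2 | Source |
|---|---|---|---|
| Coaching and pre-visit expert review | no | yes | 5.1 |
| FHQ | optional, same day, provider discretion | emailed, before the visit | 5.1 |
| Providers have seen Phase 1 counts | no | yes | 10.10.d |
| Calendar period | first 3 months | second 3 months | 5.1 |

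The date of the feedback is not given. Two 3-month phases fill the 6 months (3 + 3 = 6) with no stated gap, so feedback at the end of Phase 1 falls at or near the start of Phase 2. That is an inference.

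**2. What can be estimated**

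Let C, F, B and T be the contributions of coaching with expert review, FHQ change, feedback, and time. Then

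Phase 2 mean − Phase 1 mean = C + F + B + T.

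That is one observed contrast for four unknowns. As a check, take a design matrix with 60 patients per phase and columns for the intercept, coaching, FHQ and feedback, each of the last three coded 0 in Phase 1 and 1 in Phase 2. It has rank 2 with 4 columns. Replacing the three component columns with a single package column gives rank 2 with 2 columns. The package contrast is therefore estimable (with T still inside it), and C alone is not. More patients do not change the rank.

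**3. The FHQ and the denominator (illustration)**

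From the protocol: 60 per phase, which 2.7 lists (as 60/120) under maximum desired numbers. Assumed, not in the protocol: 12 patients meet criteria without the FHQ; a further share s meet them only through family history; FHQ completion c is 30% in one phase and 90% in the other; 6 of the 12 are referred in both phases, so coaching has no effect.

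Eligible count = 12 + 60 × s × c.

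*Case A: no patient found through the FHQ is referred.* Referred share = 6 / eligible.

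| s | Eligible, c = 30% | Eligible, c = 90% | Difference | Share, c = 30% | Share, c = 90% | Shift |
|---|---|---|---|---|---|---|
| 5% | 12.9 | 14.7 | 1.8 | 46.5% | 40.8% | 5.7 points |
| 10% | 13.8 | 17.4 | 3.6 | 43.5% | 34.5% | 9.0 points |
| 20% | 15.6 | 22.8 | 7.2 | 38.5% | 26.3% | about 12 points |

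*Case B: patients found through the FHQ are referred at the same 50% (6 of 12).* Referred share = 0.5 × eligible / eligible = 50% at every c, so the shift is 0 points. The number referred still moves, by half the change in eligible patients: 0.9, 1.8 or 3.6.

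Which phase has the higher completion is unknown. Swapping them reverses every sign.

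**4. The uniformity statement**

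Section 5.1 says OMC gathers the same patient information in both phases, with the same storage, ID assignment and distribution. 10.10.c adds that one coordinator tracks the results. The only departure in data collection shown here is the timing and mode of the FHQ.

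**The case against.** The strongest reply is that 5.1 does not claim coaching alone. It names quality improvement in the same sentence, and it lists the emailed FHQ as the first step of the tiered intervention, so coaching may be shorthand for the package. The aims in 1.5 (develop the workflow, measure uptake, document outcomes) include none that isolates coaching. Finding more eligible patients through an earlier FHQ serves the first aim and is not plainly a bias. Discussing counts with providers could itself be called coaching. This is also a pilot quality improvement study on an IRB form, and caveats on interpretation often sit in an analysis plan or report.

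Much of this stands. A reader might infer that every difference would be reported as a coaching effect and nothing else. The text does not support that, because the second purpose is stated and is sound. A reader might also infer that the FHQ change will distort the referred share by 6 to 12 points. That result needs the extreme assumption that no patient found through the FHQ is referred, and it vanishes under equal referral. 5.1 specifies counts rather than proportions; the denominator issue comes from the nesting in 10.10.d.

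What does not fall away is that 5.1 names coaching effectiveness as a measured quantity, 2.7 glosses the intervention as coaching, and neither mentions the feedback. An analysis plan could not separate components that switch on together.

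**Conclusion.** The point holds in a limited form. The comparison supports a statement about the before-after change under the combined Phase 2 package, subject to time trends. It does not support a statement about the effectiveness of coaching as such. This conclusion rests on the design as written (one site, up to 6 providers, no concurrent control), not on assumed rates. The FHQ part stands without the inferred feedback date.

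The direction and size of any distortion cannot be determined from the protocol. The illustrative range for the referred share is 0 to about 6, 9 or 12 points for s = 5%, 10% or 20%, in either direction, and depends wholly on the stated assumptions.

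The uniformity statement in 10.10.c is incorrect for the FHQ only. A reader might take this as undermining the reliability of all the collected data; the common handling described in 5.1 does not support that. Severity is minor to moderate: the wording affects what may be concluded, but no redesign of the pilot is called for.

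**What to change.** Three wording changes:

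1. **Section 5.1, end of the Phase 2 text.** State that the comparison with Phase 1 estimates the before-after change under the combined Phase 2 package (pre-visit FHQ, expert review and coaching, and feedback of Phase 1 counts), subject to time trends, and that it does not isolate the effect of coaching.
2. **Section 2.7, Phase 2 group.** Describe the intervention as the same package.
3. **Section 10.10.c.** Add to the statement on uniform processes the exception that FHQ timing and mode differ between phases: optional and same-day in Phase 1, emailed before the visit in Phase 2.

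The cost is an edit to three sections, with no new data and no change in procedures. No change to the timing of feedback is asked for. Holding it back would delay the providers' use of the Phase 1 counts by about 3 months, and the FHQ change and calendar time would still be tied to coaching.
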